
Implicit Memory Recall Test: Extinction recall may be contextually confounded by the "drug-state" during training, which would enhance spontaneous recovery (rather than enhance recall as predicted). To address this

issue, a neutral memory test sensitive to encoding-retrieval state differences will be administered during Visit 3. Following the design of Duarte et al.¹³⁵, participants will be shown a series of black and white line drawings of single objects and will be asked to decide if the object would fit into a shoebox or not, and next day (Visit 4) testing will be done using implicit cued recall and remember/know procedures to determine whether THC during encoding produces a shift from recollection to familiarity-based memory processing in accordance with state-dependent effects.

Resting State Task: During this task subjects will look at a white fixation cross on a black background for approximately 10 minutes and will be instructed to relax, keep their eyes open and on the fixation cross and clear their mind. This task allows us to investigate brain activity and drug effects independent of task-based activation.

During times when no experimental events are scheduled, subjects will be free to engage in recreational activities (e.g. read). The session will end approximately 4 hours after the drug is ingested (duration of psychoactive effects is 4 to 6 hours). However, subjects may be asked to remain in the laboratory if they still exhibit observable signs of intoxication or self-rated "high." Subjects agree in the consent form not to take any other drugs, or to operate a motor vehicle for at least 12 after the experimental session. Subjects are instructed not to drive and should arrange alternate transportation through a family member/friend or a taxi will be arranged to take them home.

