C.3.3.2. Mood & Drug Effect Questionnaires: Standardized questionnaires will be used to assess mood states and subjective drug effects throughout Visit 3, when the drug/placebo is administered. These questionnaires are sensitive to the effects of a variety of psychoactive drugs on affective state/mood and drug liking^{139,140}: (1) Visual Analog Scales (VAS); and (2) Drug Effects Questionnaire (DEQ); (3) Addiction Research Center Inventory (ARCI); (4) Spielberger Trait/State Anxiety Inventory (STAI); see below for details. In addition, physiologic measures (HR, BP) will be collected at regular intervals throughout Visit 3. At completion of the extinction session, participants will complete the End of Session Questionnaire (ESQ) which asks them to identify the substance they thought they received (e.g., THC or placebo), and to rate how much they liked its effects. They will be also asked to comment on any unusual effects they experienced, and whether they would take the substance again. These psychological and physiological measures are collected immediately before capsule ingestion (Time 0), and 30, 60, 120, 180, and 240 minutes afterwards, unless otherwise specified (e.g., DEQ will also be collected at 90 and 150min, ESQ only at 240min). Because the effects of the drugs may have a lingering effect, measures of the effects of the drug (DEQ) and review of adverse events will also be collected for exploratory purposes at two additional times: 8 hours after drug administration and the day (24 hours later) following their participation in the extinction session.

Primary subjective outcome measures will include the VAS ratings of how much participants "feel" the drug effect, and the ARCI M Scale. Secondary measures will include ratings on other self-report scales.

A. Visual Analog Scales (VAS): The VAS consists of visual analog scales used to describe current drug effects. This particular form consists of seven 100-mm horizontal lines each labeled with an adjective ("stimulated," "high," "anxious," "sedated," "down," "hungry," and "nauseated"). The left end of each line is labeled "not at all" and the right "extremely." Participants are instructed to place a mark on each line indicating how they feel at the moment.

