D.3. Termination Criteria: Participants may be terminated for any of the following: 1) alcohol or drug or psychoactive medication use that would interfere with dronabinol; 2) non-compliance with study protocol requirements; 3) development of an illness requiring that would exclude participation. Participants will be asked to withdraw from the study if they fail to appear for a session. It is imperative to the study that the sessions are consecutive and failure to appear during one of the sessions makes the data unusable. We will make every effort to ensure that the sessions are accessible (i.e., scheduling sessions during evening and weekend hours).

D.4. Sources of Materials: Research materials include the information that is obtained from the subjects from the diagnostic assessments/symptom-related interviews and questionnaires, clinical examinations including

medical history and mental health history data, behavioral data on performance on the behavioral tasks, and MRI, including structural/anatomic and functional raw data. These measurements will be performed solely for the purposes of research. All research materials will be maintained in strict confidentiality.

D.4.1. Clinical Evaluation/Participant Materials: The interview forms, paper and pencil questionnaires, and the laboratory assessment forms will be labeled with a participant code (not participant name) that is not readily identifiable to non-study staff. These forms will be kept in a locked cabinet where only official study staff can have access. All information obtained during the course of this study is strictly confidential. Our study staff will not divulge any information about interviews or other tests to non-study staff personnel. Data that may be reported in scientific journals will not include any information that identifies any person as a participant in this study.

D.4.2. Psychophysiological and fMRI: Data collected from SCR, US expectancy, and fMRI for each participant will be saved with a research identifier number only and stored in computer files without reference to any personally-identifiable information.

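### D.3 calls the data unusable after any missed session, although a dosed participant who misses only Visit 4 has already supplied the Visit 3 outcomes

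*Combined protocol and SAP*

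**What the plan says.** D.3 (Termination Criteria) gives one rule for every session: "Participants will be asked to withdraw from the study if they fail to appear for a session". The reason offered is that sessions must be consecutive and that "failure to appear during one of the sessions makes the data unusable". The rule has no exception after dosing, and the word data is not limited to particular outcomes. The sample-size text points the same way: C.2 counts failure to complete all sessions among the reasons for unusable data, and C.6 bases power on participants who complete the whole protocol with usable fMRI and SCR data.

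C.3.3.2 places drug-effect outcomes at Visit 3. It states that "Primary subjective outcome measures will include the VAS ratings" of how much the drug is felt, together with the ARCI M scale, and it schedules readings from capsule ingestion to 240 minutes. C.3.3 also puts extinction-phase SCR, US expectancy and SUDS, the Emotional Regulation Task and a resting-state scan at Visit 3. Of the resting-state scan it says: "This task allows us to investigate brain activity and drug effects independent of task-based activation".

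C.3.3.2 adds a DEQ and adverse event review, described as exploratory, at two later times: "8 hours after drug administration and the day (24 hours later) following their participation in the extinction session". C.3.4 holds the recall test (Visit 4) 24 hours after extinction learning.

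**The concern.** Someone who misses Visit 2 or Visit 3 has taken no capsule and has no drug outcome to lose. Someone who misses only Visit 4 has been randomised and dosed and has finished the Visit 3 measurements. D.3 does not distinguish the two.

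Two things are at stake. First, if D.3 is followed as written, a Visit 3 comparison of THC with placebo would include only those who came back the next day. That discards usable observations and selects the sample on an event after dosing. D.5.4 lists panic attacks, anxiety, paranoid reaction, nausea and vomiting as possible effects of dronabinol, so a link between the drug and non-attendance is conceivable. C.4.1 and C.5.1 plan no missing-data handling or report of attrition by arm that would reveal one. Second, the 24-hour adverse event review falls due on the day when the absent participant is asked to withdraw, so next-day events could go unrecorded.

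**Working it through.** **Inputs.** 150 enrolled, about 30 of them (5 in each of 6 groups) expected to be unusable through incomplete sessions or poor skin conductance, with no split given (C.2); 120 usable (D.1); half of participants assigned to dronabinol (C.3.3.1); visit content and timing (C.3.3, C.3.3.2, C.3.4).

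**1. The plan's own figure.** 150 − 30 = 120, which matches D.1. The loss is 30/150 = 20%, and 120/(1 − 0.20) = 150. This is the only stated figure that the missed-session rule feeds into, and it reproduces.

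**2. Which outcomes need Visit 4.**
- They need it: extinction recall, fear renewal, the test half of the memory task (encoded at Visit 3, tested next day), and the 24-hour DEQ and adverse event review if that is taken at the visit.
- They do not: subjective drug-effect ratings and ARCI M to 240 minutes, extinction-phase SCR, US expectancy and SUDS, the Emotional Regulation Task, and resting state. The 240-minute reading coincides with the end of the visit: "The session will end approximately 4 hours after the drug is ingested".

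So unusable is right for the first list and too broad for the second.

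**3. Range of N for Visit 3 outcomes if the data are kept.** Let x be the number of the 30 who are lost only at Visit 4; the documents do not give x. If the other losses have no usable Visit 3 data, N = 120 + x, from 120 (x = 0) to 150 (x = 30). Per drug arm, pooled over the three groups, that is 60 to 75. N for recall stays at 120.

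**4. Precision.** The standard error of a difference in means, in SD units with n per arm, is sqrt(2/n).
- Upper bound, x = 30. Kept: sqrt(2/75) = 0.163. Dropped: sqrt(2/60) = 0.183. Ratio sqrt(75/60) = 1.118, about 12% higher under the rule.
- x = 10, the other 20 having usable Visit 3 data. Kept: 75 per arm, 0.163. Dropped: 70 per arm, sqrt(2/70) = 0.169. Ratio sqrt(75/70) = 1.035, about 4%.
- x = 10, the other 20 having none. Kept: 65 per arm, sqrt(2/65) = 0.175. Dropped: 60 per arm, 0.183. Ratio sqrt(65/60) = 1.041, again about 4%.

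For an assumed standardised difference of 0.5 (not a figure from the plan) and a two-sided 5% t-test, power is 0.860 at 75 per arm and 0.775 at 60, which again is the upper-bound case.

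These figures assume equal loss in the two arms. They measure lost precision only, not the bias that unequal, drug-related loss could cause.

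**5. The 24-hour review.** C.3.3.2 sets it for the day after extinction, and C.3.4 puts Visit 4 on that day. D.3 asks the absent participant to withdraw. D.5.8 has adverse events reported to the PI and followed until resolved. No section says whether, or how, the scheduled review takes place after a missed Visit 4.

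**The case against.** For the trial's stated questions, D.3 is right. All nine hypotheses under the three aims concern the recall test, and the group-by-drug tests specified in C.4.1 and C.5.1 are of recall or renewal. The Visit 3 outcomes have no hypothesis and no written test; C.3.3.2 names primary subjective measures but gives no analysis. The demand for consecutive sessions reflects the sequence of acquisition, extinction and 24-hour recall, and D.3 can be read as speaking of that sequence alone. This stands, and it limits the importance of the point. It does not answer the wording, which has no such limit.

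A reader might infer more than the documents support in four respects.
- *That Visit 3 records will be deleted.* D.3 orders no deletion and defines no analysis set, and D.5.1 has all subject data kept in databases. Exclusion from analysis follows from the wording of D.3, with C.2 and C.6, if it is applied literally.
- *That every drug outcome is complete at Visit 3.* The memory test and the late DEQ are not. The rating of feeling the drug, named as a VAS measure, is also not among the seven VAS adjectives; the matching item is on the DEQ, which continues to 8 and 24 hours. The readings to 240 minutes are complete in either case.
- *That safety review stops.* D.3 does not say so. The 8-hour review already falls after the session of about 4 hours, so contact outside a visit is foreseen. D.5.2 gives participants staff telephone and pager numbers and encourages them to report symptoms, and D.5.8 follows events until resolved. The gap is one of silence. It remains because follow-up begins only once an event is known, and the 24-hour review is a scheduled way of finding one.
- *That absentees stayed away because of the drug, so that dronabinol would look better tolerated than it was.* Nothing in the documents shows this, and nothing rules it out.

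**Conclusion.** The point holds as a fault of wording with limited consequences. D.3 should not call all data unusable when only Visit 4 is missed, because the Visit 3 outcomes are already collected and do not depend on it. Followed as written, the rule raises the standard error of a pooled Visit 3 contrast by at most about 12%, and more plausibly by a few percent. The ceiling requires all 30 expected losses to be Visit 4 absences, although C.2 counts poor skin conductance and missed sessions together. Bias in Visit 3 comparisons, and under-recording of next-day events in one arm, are possible but not shown; their direction and size cannot be derived from the documents. The recall and renewal analyses, which carry the hypotheses, are unaffected. Severity: minor.

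**What to change.** - In D.3, say that a missed Visit 4 makes only the recall, renewal and memory-test data missing. The rule for a missed Visit 2 or Visit 3 can stay.
- Keep Visit 1 to 3 data, and analyse Visit 3 endpoints in everyone dosed who has usable Visit 3 data.
- Report Visit 4 non-attendance, with reasons, by group and drug.
- Reconcile C.3.3.2, D.3 and D.5.8 so that the scheduled 24-hour DEQ and adverse event review is still obtained when Visit 4 is missed, for example by telephone. D.5.6 already uses follow-up calls after anxiety or panic in the scanner.

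The cost is a few sentences of protocol text, a short call for each absentee, and slightly different numbers for Visit 3 and Visit 4 endpoints.

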D.5.3. Diagnostic/Phenomenological Procedures: The structured diagnostic interviews and questionnaires may contain questions that concern behaviors and thoughts that may be embarrassing or sensitive in nature. Interviews will be conducted by experienced mental health workers that will maintain confidentiality and all data from interviews and questionnaires will be numbered to help conceal the identity of the participant. All participants will be informed that they are free to take a break at any time during the clinical interviews and questionnaires if they become bored, tired, or otherwise agitated. Participants will also be informed that they can refuse to answer any question that they feel is too personal or distressing.

D.5.4. Dronabinol related risks: Dronabinol is associated with some adverse experiences (incidence 1%-10%) including: asthenia, increases in heart rate, palpitations, facial flush, sensory impairment, headache, nausea, vomiting, dry mouth, changes in appetite, easy laughing, euphoria, restlessness, panic attacks, anxiety/nervousness, paranoid reaction, confusion, dizziness, drowsiness, and impairment in coordination. [name]., a Board-certified physician, or his physician designate and will be available during all behavioral tasks in order to evaluate and recommend further evaluation and treatment for the emergence of any adverse events/side effects.

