
The MRI scanning procedures are experimental, but they follow the guidelines established by the U.S. Food and Drug Administration for MRI scanning. Care will be taken to avoid all known risks associated with MRI. However, this procedure may involve risks that are currently not anticipated. The participants will be constantly monitored for any side effects and will be treated appropriately by physicians and nurses available. The study may be aborted if the participant has any discomfort. The safety of the participants will be continually monitored.

D.5.7. Ongoing DSMP by PI and Staff: Weekly meetings of the research staff of this study will be conducted that will include review of accrual, consenting procedures, protocol adherence, adverse events, and quality control of all data obtained from the study in the previous week. Minutes of these meetings will be recorded, signed by the PI, and archived in study's regulatory binder. All changes in protocol design will be reviewed by the IRB at WSU before such changes in protocol design take place.

D.5.8. Reporting of Adverse Events: Adverse events (AEs) will be recorded and tracked for this study. AEs will be reported per IRB and NIH/NIMH requirements. An AE is any experience that has taken place during the course of a research project, which, in the opinion of the investigators, was harmful to a subject participating in the research, increased the risks of harm in the research, or had an unfavorable impact on the risk/benefit ratio. AEs will be graded using the mild, moderate, severe terminology as defined:

Mild – Noticeable to the subject, does not interfere with the subject's daily activities, usually does not require additional therapy, dose reduction, or discontinuation of the study.

Moderate – Interferes with the subject's daily activities, possibly requires additional therapy, but does not require discontinuation of the study.

Severe – Severely limits the subject's daily activities and may require discontinuation of the study. This would include all adverse events defined as "Serious" by the IRB. The PI will assign attribution as definitely associated, probably associated, possibly associated, or unrelated. Adverse events will also be recorded as expected or unexpected.

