All adverse events (AEs) occurring during the course of the study will be reported to the PI. All AEs will be evaluated, medically treated or referred to medical treatment, and followed until resolved satisfactorily. If deemed necessary by a physician, a participant may be withdrawn from the study. AEs will be evaluated for serious adverse event (SAE) criteria. A Serious Adverse Event (SAE) is any adverse experience occurring during the study that: (a) results in death, (b) is life threatening (e.g., suicidality, homicidality), (c) results in hospitalization or prolongation of hospitalization, or (d) results in persistent disability. If a participant from the study or the PI discontinues a participant's participation due to a SAE, the participant will receive follow-up medical care as necessary. Follow-up care will continue until the participant no longer requires hospitalization, the condition is stabilized with no future change expected, the problem is determined to be unrelated to the drug used in the study, or the participant dies. Finally, if considered related to the trial, unanticipated problems involving risks to subjects or others will be reported to both the IRB and NIH/NIMH.

All SAEs and/or unexpected AEs will be reported to the IRB and NIH/NIMH within 7 days of occurrence or recognition. Fatal or life-threatening adverse events will be reported to the above institutions within 24 hours. Regular annual reviews of protocol activity and all AEs will be submitted to the IRB and NIH/NIMH. Other less serious and expected AEs will also be reported to the above institutions with compliance to their requirements.

D.5.9. Persons responsible: At Wayne State University PI [name], Co-Investigators, and the Project Coordinator will be responsible for overseeing data integrity, safety monitoring, and reporting of adverse events.

D.8. Payment to Subjects: Participants who complete the study will be paid up to \$110 for their participation. Participants are compensated for what they complete based on the following breakdown: \$30 for Visit 1; \$10 for Visit 2; \$50 for Visit 3; \$20 for Visit 4

D.9. Potential Benefit of the Proposed Research to Human Subjects and Others: There will be no direct benefit to participants for participation in this study, other than; they will be compensated for their time for participation in this study. There will be no cost to participants associated with participation in this study other than transient discomfort.

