D.10. Importance of the Knowledge to be Gained: The risks involved in this study are minimal when compared to the benefits gained. Benefits to society include the potential for increased knowledge regarding the effects of the cannabinoid system on emotional memory and the brain, which may help us treat anxiety disorders.

such as PTSD. Current knowledge from studies in animal models and healthy humans of aversive learning and memory suggest that THC facilitates the extinction of fear memories after a traumatic event. The use of Marinol®, a synthetic form of THC, in PTSD patients may also provide similar effects and if so, will prompt the development of clinical trials in which dronabinol is used as an adjunct to exposure-based therapies to facilitate treatment in patients with anxiety disorders. Currently Marinol® is prescribed to humans to treat anorexia associated with weight loss in patients with AIDS and nausea and vomiting associated with cancer chemotherapy. We expect that the medication when given only once at the specified dose (7.5 mg) in a closely monitored laboratory setting will be well tolerated by participants without SAEs and carries little risk for development of subsequent problems including abuse/dependence. This expectation is supported by the fact that we have not had any SAEs with this dose and design in our past extinction studies in healthy humans^{95,137}. We believe that the risks are minimal and the benefits are substantial.

E. Bibliography and References Cited

- 1 Rauch, S. L., Shin, L. M. & Phelps, E. A. Neurocircuitry models of posttraumatic stress disorder and extinction: human neuroimaging research--past, present, and future. *Biol Psychiatry* **60**, 376-382, doi:S0006-3223(06)00796-7 [pii] 10.1016/j.biopsych.2006.06.004 [doi] (2006).
- 2 Rosen, J. B. & Schulkin, J. From normal fear to pathological anxiety. *Psychol Rev* **105**, 325-350 (1998).
- 3 Foa, E. B. Prolonged exposure therapy: past, present, and future. *Depress Anxiety* **28**, 1043-1047, doi:10.1002/da.20907 (2011).
- 4 Hofmann, S. G. Cognitive processes during fear acquisition and extinction in animals and humans: implications for exposure therapy of anxiety disorders. *Clinical Psychology Review* **28**, 199-210 (2008).
- 5 Bouton, M. E. Context and behavioral processes in extinction. *Learn Mem* **11**, 485-494 (2004).
- 6 Myers, K. M. & Davis, M. Mechanisms of fear extinction. *Mol Psychiatry* **12**, 120-150 (2007).

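### D.5.8 makes adverse-event status depend on the investigators' opinion of harm, which conflicts with its own Mild and expected categories and may leave non-serious AE counts incomplete

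*Combined protocol and SAP*

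**What the plan says.** D.5.8 defines an AE as an experience during the project "which, in the opinion of the investigators, was harmful to a subject participating in the research", or that "increased the risks of harm in the research, or had an unfavorable impact on the risk/benefit ratio". The reference to opinion governs all three alternatives.

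The later steps in D.5.8 apply to events already classed as AEs:
- The Mild grade is "Noticeable to the subject, does not interfere with the subject's daily activities".
- The PI assigns attribution, and "Adverse events will also be recorded as expected or unexpected".
- On reporting, "Other less serious and expected AEs will also be reported to the above institutions", in line with those bodies' requirements.

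D.5.4 says "Dronabinol is associated with some adverse experiences (incidence 1%-10%) including" and then lists 20 reactions, from asthenia to impaired coordination.

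C.3.3.2 collects heart rate, blood pressure, VAS, DEQ, ARCI and STAI in every participant at 0, 30, 60, 120, 180 and 240 minutes, with extra DEQ times. The End of Session Questionnaire (ESQ) at 240 minutes invites comment on unusual effects. A review of adverse events follows at 8 and 24 hours, described as exploratory. D.5.7 has adverse events reviewed at weekly staff meetings.

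D.10 expects that the single 7.5 mg dose "will be well tolerated by participants without SAEs".

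**The concern.** A definition that asks for a judgement of harm first, and grades severity second, decides what enters the safety record before anyone has described the event. A dry mouth or a facial flush fits the Mild grade exactly, but an investigator could reasonably say that it harmed nobody, added no risk and left the risk/benefit balance unchanged. Two staff members could both follow D.5.8 and record different things.

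At stake is the completeness of the non-serious AE record that is reviewed weekly and sent to the IRB and NIH/NIMH. Section A says that direct tests of cannabinoid effects on extinction recall have not been done in PTSD patients, and D.10 rests its expectation on earlier extinction studies in healthy people. Mild and moderate reactions in the PTSD group would therefore be useful information. C.3.3 also anticipates that some participants will show observable signs of intoxication. Staff forming the opinion may therefore be able to guess the arm, which could affect any descriptive comparison of AEs between dronabinol and placebo.

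**Working it through.** The plan gives no sample size, power or precision figure for safety, so there is no stated figure to reproduce. The check sets the provisions side by side and then counts coverage.

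**1. Does anything else in the plan settle the definition?**
- *Mild grade, expected label, reporting of expected AEs (D.5.8).* These suggest that the authors want minor expected reactions recorded. Each applies only once an event is an AE, so they show the inconsistency without resolving it.
- *D.5.4.* It calls the listed reactions adverse experiences with no test of harm.
- *D.5.6.* It says peripheral nerve stimulation may be mildly uncomfortable but does no harm. In the protocol's own usage, then, a mild discomfort can fall outside the first alternative of the AE definition.
- *AE reviews at 8 and 24 hours (C.3.3.2) and weekly (D.5.7).* These review adverse events, so for AEs they inherit the definition. No symptom checklist is described.

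**2. Which listed reactions are measured whatever the AE definition?** The matching is a judgement, so a strict and a loose count are given.
- *Strict match, 6 of 20 (30%):* increased heart rate (HR); nausea (VAS); appetite change (VAS hungry, increase only); euphoria (ARCI MBG scale, VAS high); anxiety/nervousness (VAS anxious, STAI); drowsiness (VAS sedated, ARCI PCAG scale).
- *Loose match, 9 of 20 (45%):* adds palpitations (HR), restlessness (VAS stimulated) and panic attacks (VAS anxious).
- *No direct measure:* 20 − 9 = 11 to 20 − 6 = 14. On either count these include headache, dry mouth, facial flush, vomiting, dizziness, confusion, paranoid reaction and impaired coordination. Some are touched by related scales, such as the ARCI LSD scale for dysphoria and somatic symptoms, but otherwise they depend on the AE record or the ESQ comment.

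**3. How large are the counts?** C.2 plans 150 participants and C.3.3.1 gives half of them dronabinol: 150 / 2 = 75. Assume that the 1% to 10% in D.5.4 applies to each reaction.
- Expected cases per reaction with 75 dosed: 75 × 0.01 = 0.75 to 75 × 0.10 = 7.5.
- Chance of at least one case at 1%: 1 − 0.99^75 = 0.53. At 10%: 1 − 0.90^75 = 0.9996.
- C.2 expects about 30 participants without usable data. If all 30 were lost before dosing, 60 would be dosed, giving 0.6 to 6.0 cases.

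These figures show only that counts per reaction will be small, so a few missing records would change the picture. They do not estimate how many events would go unrecorded, and nothing in the documents does.

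**The case against.** The strongest reply is that the section should be read as a whole. A Mild grade needing only a noticeable event, an expected category and an instruction to report less serious expected AEs all point towards recording these reactions. IRB and NIH/NIMH requirements, which D.5.8 invokes, may also govern what must be captured. This stands as evidence of intent. A reader might infer that D.5.8 lets most listed reactions go unrecorded, but the text does not say that. It leaves the matter to opinion and points in two directions.

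A second reply is that tolerability does not rest on the AE record alone. That is correct. A reader might conclude that the D.10 expectation cannot be checked. However, D.10 words it in terms of serious events, which D.5.8 defines by outcome (death, threat to life, hospitalization, persistent disability), and the Visit 3 measures allow part of tolerability to be compared by arm. What remains open is the 11 to 14 reactions without a direct measure.

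Third, no AE comparison between arms is planned, there is no safety hypothesis, and dosing is double-blind. This also stands. Differential recording is a risk for any descriptive contrast, and its direction cannot be stated: staff might discount familiar drug effects or be more alert to them.

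Fourth, a panic reaction is a poor example of an event that might vanish. D.5.5 provides clinician evaluation during tasks, and D.5.6 provides for stopping, counselling and follow-up calls after in-scanner panic.

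Finally, D.10 should not be read as making tolerability the trigger for later adjunct-treatment trials. The trigger there is a facilitating effect on extinction.

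**Conclusion.** The inconsistency is real. D.5.8 requires an opinion of harm, added risk or worsened risk/benefit before an event is an AE, while its own Mild grade, its expected label, its reporting rule and D.5.4 all presuppose that minor, anticipated reactions are AEs. The Visit 3 measures cover about 6 to 9 of the 20 listed reactions directly, and the rest have no systematic query behind them. Non-serious AE counts may therefore be incomplete, and a descriptive contrast between arms could be affected by staff who can see signs of intoxication.

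The conclusion goes no further. Serious-event capture and the planned SCR, expectancy and fMRI analyses are untouched, and the documents do not support any estimate of the number of events lost. It rests on the matching of reactions to measures given above, and on there being no fuller AE form or symptom checklist outside the document. Severity is minor to moderate.

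**What to change.** In D.5.8, define an AE as any untoward or unintended sign, symptom or change after consent, recorded whether or not an investigator considers it harmful or related. Then apply the severity, attribution and expectedness steps already in the section. Keep the harm and risk test only for deciding what is an unanticipated problem.

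Turn the 20 reactions in D.5.4 into a checklist on the AE form. Ask it in the same words in both arms at the reviews already planned at 8 and 24 hours, covering the whole time since the capsule.

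The cost is a revised paragraph, one form and more mild AEs to log, with a less favourable AE count as a result. D.5.8 sends all unexpected AEs to the IRB and NIH/NIMH within 7 days, so a wider definition would also bring mild unexpected events under that deadline. No visit is added, and dosing and participant management do not change.
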